## Adverse Events of Hypocalcemia: Symptomatic and Asymptomatic

Adverse events consistent with hypocalcemia will be classified as either symptomatic or asymptomatic, and assessed for severity, recognizing that there is a spectrum of clinical manifestations. Symptomatic hypocalcemia will be based on identification of symptoms consistent with hypocalcemia such as numbness/tingling of hands, feet or lips, muscle cramps/spasms/twitching, other weakness or lightheadedness and/or new or worsening anxiety, including anger or depression and neurocognitive signs of confusion/hallucinations accompanied by laboratory evidence of a drop in cCa. Relevant symptoms will be documented as blood calcium levels are checked to confirm calcium status. A Case Report Form (CRF) for symptomatic hypocalcemia as an AE of special interest will capture the details of each hypocalcemic event including but not limited to symptoms, concomitant cCa concentrations, precipitating factors, treatment, resolution, and action taken regarding study medication.

Asymptomatic hypocalcemia will also be captured as an AE of special interest based on defining a threshold value for cCa < 7 mg/dL. Since cCa levels are sampled frequently throughout the inpatient period, asymptomatic low cCa results will be identified during routine cCa monitoring.

#### **Clinical Evaluation and Treatment of Hypocalcemia:**

Hypocalcemia can range in symptom severity from asymptomatic to life-threatening. Appropriate treatment and action regarding study medication and/or other interventions (e.g., urgent calcium supplementation) will primarily be based on clinical evaluation of severity and acuity. Cases of hypocalcemia in this trial, if they occur, are expected to be manageable with supportive treatment.

Different patients may have different sensitivities to low calcium levels but one advantage of conducting this initial safety and proof-of-concept trial at the NIH is that the expert investigators have significant experience in managing these patients as well as specific

historical knowledge about the clinical course and management of many members of the expected cohort to be studied. The investigators performing the current study have decades of accumulated and institutional experience caring for these patients including management of hypocalcemia that is a consequence of the underlying disorder. This includes experience managing outpatient regimens of oral calcium and calcitriol to ensure patient functioning, well-being and quality of life, based on outpatient laboratory monitoring and assessment of symptoms.

Appropriate evaluations may include serial cCa measures, an initial and follow-up ECG as appropriate based on clinical assessment (bradycardia e.g.) and/or if cCa is < 7 mg/dL.

Graded interventions according to the expert judgment of the NIH investigators will include standard measures such as oral calcium and/or calcitriol supplementation (see below) for mild-moderate events. In the case on unresolving or worsening hypocalcemia with more acute clinical manifestations including worsening neurocognitive deficits, seizures, tetany, hypotension or cardiac dysfunction, for example, appropriate urgent intervention, also according with standards of care, will be undertaken by the site, including administration of intravenous calcium gluconate (see below).

### Addition of Oral Calcium Supplements and/or Calcitriol

Since all participants will be attempting to consume at least 1000 mg dietary calcium per day throughout the trial, additional supplemental oral calcium in the range of 1,000–2,000 mg additional supplement may be given as required with close follow-up of cCa. Transient requirements for calcium supplementation and/or 1-2 doses of calcitriol (at doses based on each participant's prior known sensitivity and dosing of outpatient calcitriol, if known, e.g., likely in the range of 0.5-2 mcg) resulting in stabilized calcium levels, need not interfere with per protocol dose escalation, particularly if required on Days 1 and 2 before CLTX-305 (encaleret) effective doses may have been achieved. More severe or prolonged hypocalcemia unresponsive to oral supplementation may require early termination from the study period at the judgement of the investigator. If calcium levels are not stable and if evidence of clinically significant hypocalcemia precludes further dosing in the study period, CLTX-305 (encaleret) dosing will be stopped and participants may be re-started on their prior outpatient regimen of oral calcium and calcitriol and discharged when stable, with close follow-up. Such participants may be eligible to return for either a repeat of the study period or to the next per protocol study period, at the discretion of the investigator and the Sponsor.

## **Intravenous Calcium supplementation:**

In the event of severe hypocalcemia, the NIH Clinical Center has the facilities to conduct advanced supportive care including intravenous fluid replacement, supplemental oxygen, continuous ECG monitoring, and bedside ionized calcium monitoring if required. Intravenous calcium may be given as clinically indicated.

#### 8.5.8 Reporting of Pregnancy

Study center personnel must report every pregnancy from the time study participant signs the ICF until  $30 \pm 7$  days after the last dose of CLTX-305 (encaleret). Within 24 hours of

learning of the pregnancy, study center personnel must report the event to the Sponsor or its designated representative on the Clinical Trial Pregnancy Form, even if no AE has occurred.

The study team will make every effort to follow the pregnancy to its conclusion and report the outcome on the follow-up Clinical Trial Pregnancy Form. If the pregnancy is associated with an SAE (e.g., if the female participant is hospitalized for hemorrhage), a separate SAE Form must be completed (in addition to the Pregnancy Form) as described in Section 8.5.5 and Section 8.5.6, with the appropriate serious criterion (e.g., hospitalization) indicated.

In the event that a participant becomes pregnant, the investigator is required to contact the Sponsor Medical Monitor/designee within 24 hours of awareness.

If a participant becomes pregnant, administration of the study drug(s) must be discontinued immediately.

If the partner of a male participant becomes pregnant after initiation of CLTX-305 (encaleret) and within  $30 \pm 7$  days of the last dose, the study team will inform the Sponsor Medical Monitor/designee. If the partner agrees, the study team will amend the protocol to allow for follow-up of the pregnancy.

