The metabolism and elimination of CLTX-305 (encaleret) in preclinical studies has been conducted. Based on non-clinical data, fecal excretion was the main route of elimination. In humans, excretion of unchanged CLTX-305 (encaleret) and metabolites into urine was minimal (< 5% as total of parent and metabolite). The two major glucuronide metabolites (M1, M3) showed similar pharmacokinetics as the parent drug, with M1 median  $t_{max} \sim 2$  hr. and M3 median  $t_{max} \sim 1.5$  hr. For M1 (inactive), concentrations in plasma were approximately 2-fold higher than those of parent drug; M3 (active) concentrations were low (10% compared to parent). Neither M1 nor M3 showed prolonged elimination (see Investigator Brochure for details). CLTX-305 (encaleret) has not been formally studied in patients with severe to moderate renal impairment but significant dose adjustments in this population are not expected given elimination pathway and in the setting of the protocol dose escalation safety review process.

In a human drug interaction study, CLTX-305 (encaleret) co-administration with ketoconazole, a potent CYP3A4 inhibitor, resulted in  $\sim$ 1.67x increase in  $C_{max}$  and  $\sim$ 2x increase in AUC0-24 with slightly less effect on M1 and M3.

The potential for skin phototoxicity in humans is expected to be minimal based on the tissue distribution in rats and estimated human dosage, but participants may be at increased risk to natural or artificial sunlight (tanning beds or ultraviolet A/B light (UVA/B) treatment). Participants at increased risk to UV injury are encouraged to minimize or avoid exposure to natural or artificial sunlight (tanning beds or UVA/B treatment), wear sun-protective clothing, and use sunscreen that strongly absorbs ultraviolet A light (UVA).

It is not known if CLTX-305 (encaleret) could have an effect on pregnancy or breastfeeding in humans. CLTX-305 (encaleret) may have potential teratogenic effects in humans based on the results of a reproductive toxicity study in rabbits where the incidence of skeletal anomalies (fusion of the sternebra) was increased in the fetuses at 30 mg/kg and above. Currently, Women of child-Bearing Potential (WOCBP) will be consented to receive pregnancy testing at screening and at intervals throughout the trial and required to utilize contraception and agree to avoid pregnancy during the experimental treatment.

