### 5.2 Exclusion Criteria

Participants who meet any of the following criteria during Screening will not be eligible to participate in the study:

- 1. History of treatment with PTH 1-84 or 1-34 within the previous 3 months
- 2. History of hypocalcemic seizure within the past 3 months
- 3. Blood 25-OH Vitamin D level < 25 ng/mL
  - a. If participant has a blood 25-OH Vitamin D level < 25 ng/mL at the screening visit, they will be prescribed cholecalciferol or ergocalciferol supplementation. Once the 25-OH Vitamin D level is > 25 ng/mL, the participant will be eligible to continue to the treatment phase of the study.
- 4. Participants with hemoglobin (Hgb)  $\leq$  13 g/dL for men and  $\leq$  12 g/dL for women
  - a. If participant has a low Hgb at the screening visit due to iron, B12, or folate deficiency, they will be prescribed supplementation. Once the Hgb level is > 13 in men or > 12 in women, the participants will be eligible to continue to the treatment phase of the study.
- 5. Abnormal laboratory values which in the opinion of the investigator, would make the participant not suitable for participation in the study
- 6. Estimated glomerular filtration rate (eGFR) < 25 mL/minute/1.73 m^2 using CKD-EPI (for participants < 18 years old the Schwartz equation will be calculated)
- 7. 12-lead resting electrocardiogram (ECG) with clinically significant abnormalities
- 8. Participants with positive hepatitis B surface antigen (HBsAg), Hepatitis A immunoglobulin M (IgM), or human immunodeficiency virus (HIV) viral serology test results at the Screening Visit. Participants who are in complete remission from Hepatitis C as evidence by sensitive assay ≥12 weeks after completion of HCV therapy are allowed to participate in the study.

- 9. Pregnant or nursing (lactating) women, where pregnancy is defined as the state of a female after conception and until the termination of gestation, confirmed by a positive serum hCG laboratory test
- 10. Women of child-bearing potential, defined as all women physiologically capable of becoming pregnant, unless they are using highly effective methods of contraception during dosing and for 3 months following the discontinuation of study treatment. Highly effective contraception methods include:

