  - Total abstinence (when this is in line with the preferred and usual lifestyle of the participant). Periodic abstinence (e.g., calendar, ovulation, symptothermal, post-ovulation methods) and withdrawal are not acceptable methods of contraception.
  - Female sterilization (have had surgical bilateral oophorectomy with or without hysterectomy) or tubal ligation at least six weeks before taking study treatment. In case of oophorectomy alone, only when the reproductive status of the woman has been confirmed by follow up hormone level assessment.
  - Male sterilization (at least 6 months prior to screening). For female participants on the study the vasectomized male partner should be the sole partner for that participant.
  - Combination of the following (a+b or a+c, or b+c):
    - a. Use of oral, injected or implanted hormonal methods of contraception or other forms of hormonal contraception that have comparable efficacy (failure rate <1%), for example hormone vaginal ring or transdermal hormone contraception
    - b. Placement of an intrauterine device (IUD) or intrauterine system (IUS)
    - c. Barrier methods of contraception: Condom or Occlusive cap (diaphragm or cervical/vault caps) with spermicidal foam/gel/film/cream/vaginal suppository
- 11. Sexually active male participants who are unwilling to use a condom during vaginal intercourse while taking the CLTX-305 (encaleret) (study drug) and for 3 months after the last dose of the study drug. Participants should not father a child during active participation in the study starting with the first CLTX-305 (encaleret) dose in Period 1, Period 2 (for Cohort 2) until the end of study participation. Condoms are not required if the participant is vasectomized or if the participant's partner is not a woman of child-bearing potential.
- 12. Hypersensitivity to any active substance or excipient of CLTX-305 (encaleret)
- 13. History of drug or alcohol dependency within 12 months preceding the Screening Visit
- 14. History of thyroid or parathyroid surgery
- 15. Current participation in other investigational drug studies
- 16. Unwillingness to refrain from blood donation within 12 weeks prior to screening visit from the start of the study enrollment through one year after the last dose of the study drug

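### Contraception is required for 3 months after the last dose, but pregnancies must be reported only until 30 ± 7 days after it; Protocol 5.2, 2.3.1 and 8.5.8 need reconciling

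*Protocol*

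**What the plan says.** **Reporting.** Protocol 8.5.8 sets the start: "Study center personnel must report every pregnancy from the time study participant signs the" consent form. The end is 30 ± 7 "days after the last dose of CLTX-305 (encaleret). Within 24 hours of" learning of a pregnancy, the site must send a form to the sponsor. A separate sentence covers partners of male participants: if the pregnancy begins after the first dose and within 30 ± 7 "days of the last dose, the study team will inform the Sponsor Medical Monitor/designee". A further sentence requires contact with the medical monitor within 24 hours of awareness that a participant is pregnant; that sentence has no end date.

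**Contraception.** Exclusion criterion 10 (Protocol 5.2) admits women of child-bearing potential only if they use highly effective methods "during dosing and for 3 months following the discontinuation of study treatment". Criterion 11 requires condom use by sexually active men while on drug and "for 3 months after the last dose of the study drug". The same criterion bars fathering a child only until the end of study participation.

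**Reason given.** Protocol 2.3.1 says the drug "may have potential teratogenic effects in humans based on the results of a reproductive toxicity study in rabbits". The same paragraph says women of child-bearing potential are "required to utilize contraception and agree to avoid pregnancy during the experimental treatment"; it does not mention the 3-month tail.

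**Related provisions.** A congenital anomaly is a seriousness criterion (8.5.2). Serious adverse events assessed as related stay reportable beyond 30 days (8.5.6). Section 8.2.5 makes the last scheduled contact a call at 30 ± 7 days, and it also provides for participants who stop the drug in the extension for family planning.

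**The concern.** One section asks participants to prevent conception for 3 months after stopping; another stops asking about conception after roughly one month. A pregnancy conceived on day 60 would breach the contraception condition, yet no dated rule requires the site to report it or to follow it to its outcome. The mismatch applies to women in the trial and to partners of men in the trial.

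What is at stake is safety information. Protocol 2.3.1 says the effect on human pregnancy is not known, and the documents describe no human pregnancy data. With up to 16 participants treated, any pregnancy soon after stopping would be a rare observation. Normal outcomes matter as well as abnormal ones, because without them there is no denominator. Such conceptions are foreseeable: 8.2.5 expects that some participants may stop in order to start a family.

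The cut-off is also loosely defined. For participants, 8.5.8 does not say whether it refers to the date of conception or the date the site becomes aware. The schedules in Tables C and D place pregnancy tests at clinic visits but none in the follow-up columns, so a conception close to the last dose could be recognised only after reporting has closed.

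**Working it through.** The plan states no figure on this point, so there is none to reproduce. The check is a comparison of two periods counted from the last dose.

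**Inputs**

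| Quantity | Value | Source |
|---|---|---|
| Post-dose contraception period, C | 3 months; taken as 90 days, also 84 (12 weeks) and 92 | Protocol 5.2, criteria 10 and 11; the conversion to days is an assumption |
| Post-dose reporting period, R | 30 days, range 23 to 37 | Protocol 8.5.8 |

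**Formula.** Days without a dated reporting requirement = C − R. Share of the post-dose contraception period = (C − R) / C.

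| C | R = 23 | R = 30 | R = 37 |
|---|---|---|---|
| 84 days | 61 (72.6%) | 54 (64.3%) | 47 (56.0%) |
| 90 days | 67 (74.4%) | 60 (66.7%) | 53 (58.9%) |
| 92 days | 69 (75.0%) | 62 (67.4%) | 55 (59.8%) |

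So about 60 of 90 days are uncovered, with a range of 53 to 67. How 3 months is converted to days makes little difference; the ± 7-day tolerance contributes more.

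**Denominator.** These shares refer only to the tail after the last dose. The contraception requirement also covers dosing, and pregnancies during dosing are reportable. For 24 weeks of Period 3 plus the tail, the period is 168 + 90 = 258 days, and 60 / 258 = 23%. Adding a 25-month extension (25 × 30.4 = 760 days) gives 168 + 760 + 90 = 1,018 days, and 60 / 1,018 = 6%.

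**A conception on day 60, taken through the rules**

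- Criteria 10 and 11: inside the contraception period.
- 8.5.8, dated rule for participants: outside.
- 8.5.8, partner rule: outside, with its own explicit 30 ± 7-day limit.
- 8.5.8, undated 24-hour sentence: arguably covers a participant; does not cover a partner.
- 8.5.2 with 8.5.6: reached only if the outcome is serious, the site learns of it, and the investigator judges it related.

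An uneventful late pregnancy, or one with an outcome not judged related, is therefore caught at most by the undated sentence, and in a partner by none of these rules.

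**The case against.** The strongest case is that the two periods need not match. Protocol 2.2.1 gives a steady-state half-life of about 11 to 14 hours and no prolonged elimination of the two main metabolites. At 14 hours, day 23 is 23 × 24 / 14 = 39 half-lives and day 60 is 103. A contraception rule may carry a precautionary margin without making every conception within it an exposed one, and 2.3.1 mentions contraception only during treatment. The 30 ± 7-day limit also matches the adverse event collection period (8.5.5) and the last follow-up call (8.2.5).

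Much of this stands. A reader might infer that the protocol treats 3 months as an at-risk window, or regards a day-60 conception as exposed. The documents say neither: criteria 10 and 11 give no rationale for the 3 months, and the half-life argues against drug exposure at day 60. A reader might also infer that two thirds of the whole risk period goes unreported. That fraction belongs only to the post-dose tail, and what is missing there is a dated requirement; reporting is not forbidden. Nor can one say that such pregnancies would be the only human evidence, since the investigator's brochure and the Phase 3 protocol are not available here.

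Few people are affected. SAP 13.7.1 records no early discontinuations through Period 3 Week 24, and participants who move to the Phase 3 extension keep dosing until they enrol there (Protocol 7.2).

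What does not stand is the suggestion that the other provisions close the gap. The late-event route depends on a judgement of relatedness and on someone learning the outcome, and partner pregnancies have an express cut-off. A short half-life may explain a 30-day reporting limit, but the protocol does not offer it as a reason, and it leaves the 3-month rule in 5.2 unexplained.

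**Conclusion.** The point holds as an inconsistency among Protocol 5.2, 2.3.1 and 8.5.8. About 60 days (53 to 67 of 90, or 59% to 74%) of the contraception period after the last dose have no dated requirement to report a participant or partner pregnancy. This rests on reading 3 months as 90 days and on the stated tolerance.

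Its practical reach is modest. It concerns only people who stop the drug, including those who stop for family planning, and the related birth defect that would matter most remains reportable if it comes to light. The loss is in pregnancies that are uneventful or not judged related, mainly those of partners. No efficacy result or estimate in the SAP depends on it. Which contraception duration is clinically right is not judged here.

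**What to change.** Reconcile the three sections by a wording change:

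- In 8.5.8, make the reporting period for participant and partner pregnancies at least as long as the post-dose contraception period the protocol sets.
- Bring the description of the contraception period in 2.3.1 into line with 5.2, so that 8.5.8 has one duration to refer to.
- State in 8.5.8 whether the cut-off refers to the date of conception or the date the site becomes aware, and whether the undated 24-hour sentence falls under the same limit.

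This is a cheap improvement. Against the present 3-month rule, the site would accept reports for about two months beyond the last scheduled contact. Because no later contact is planned, this would be passive reporting: participants would be asked at the final call to notify the site of a later pregnancy. It needs no new visits or tests, and it would bring the uncovered part of the post-dose contraception period to zero.

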## **8.6** Unanticipated Problems

# 8.6.1 Definition of Unanticipated Problems (UP)

Any incident, experience, or outcome that meets all the following criteria:

- Unexpected in terms of nature, severity, or frequency given (a) the research procedures that are described in the protocol-related documents, such as the Institutional Review Board (IRB)-approved research protocol and informed consent document; and (b) the characteristics of the participant population being studied; and
- Related or possibly related to participation in the research ("possibly related" means there is a reasonable possibility that the incident, experience, or outcome may have been caused by the procedures involved in the research); and
- Suggests that the research places participants or others (which many include research staff, family members or other individuals not directly participating in the research) at a greater risk of harm (including physical, psychological, economic, or social harm) than was previously known or expected.

## 8.6.2 Unanticipated Problem Reporting

The investigator will report unanticipated problems (UPs) to the NIH Institutional Review Board (IRB) as per Policy 801 and to the Sponsor.

## 8.6.3 NIH Intramural IRB Reporting of IND Safety Reports

Only IND Safety Reports that meet the definition of an unanticipated problem will need to be reported to the NIH Intramural IRB.

## 9 STATISTICAL CONSIDERATIONS

All analysis details will be provided in a formal statistical analysis plan (SAP).

## 9.1 Statistical Hypothesis

All data will be descriptively analyzed with no hypothesis testing.

